The patient will emerge from anesthesia for clinical placement of the left DBS electrode and neurological testing done by [name] and the neurologist. Once clinical testing is complete, the ECoG strip will be placed on the right side for research purposes. Then, [name] will continue with the clinical procedure and place the right DBS electrode and conduct neurological testing to confirm placement. The researchers will connect ECoG and DBS leads to the Neuro-Omega system to record brain signals throughout research related tasks. Once all clinical testing has been completed, the research team will simultaneously record cortical ECoG and pallidal LFP from GPI/GPe during both induction and emergence with target-controlled infusion of propofol detailed above. During induction and emergence, the participant will also complete the behavioral task detailed above. If data is being collected for **Specific Aim 2**, ECoG /LFP recordings and behavioral assessments will take place with no stimulation. If data is being collected for **Specific Aim 3b**, recordings and behavioral assessments will be made during both induction and emergence of anesthesia with either GPI or GPe stimulation. When the research portion is complete, the ECoG strips will be removed and the surgery will finish per clinical standard of care.

DATA ANALYSIS

LFP Analyses:

Signal analysis is performed in MATLAB (The Mathworks Inc., Natick, MA). Data is parsed into various behavioral and stimulation state epochs, excluding any sections containing electrical or movement artifact using methods previously described.^{41, 50} Bipolar re-referencing of adjacent contacts is used in order to emphasize local and minimize global signals, which is critical for the proposed network coupling analyses across brain regions. 60 Hz line noise is rejected using a notch filter. 60 Hz line noise is rejected using a notch filter.

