Measures of Network Coupling (bivariate, assessed over time and trials) In our approach, when we refer to analyzing "network coupling," we will investigate a broad range of coupling measures. The measures and their rationale are summarized here. Coherence, the most commonly used measure of LFP coupling, is used to describe the degree of co-variability between signal pairs over different frequency ranges.⁶¹ To find the time-frequency representation of coherence for pairs of signals, we use a moving window approach and multi-taper method. Phase synchrony index, a measure of consistency of phase differences between two signals, is used to separately evaluate the specific role of phase difference on neurophysiological observations. Phase locking is of particular interest as fixed phase relationships may be particularly detrimental to information transfer across nodes.⁶² Phase-Amplitude Coupling (PAC) is assessed both locally and across nodes and across time and across trials and is quantified using modulation index (MI).⁶³ PAC is a critical measure that has been identified as a putative pathophysiological mechanism and our group has previously shown to be a potential mechanism for long distance coordination of physiological signals.¹⁶ MI is a method based on Kullback-Liebler (KL) divergence used to extract PAC, described previously. In order to extract the phase from phase signals corresponding to the peak of amplitude signal which we refer to as preferred phase, the weights of the phaseamplitude histogram were used as amplitudes of a vector, while the center phase of each bin constituted the phase of the vector. Statistical significance of MI values is evaluated using surrogate data analysis (by circularly shifting one series relative to the other). MI values are then converted into z-scores and false discovery rate (FDR) is used to correct p-values for multiple comparisons.⁶⁴ Phase lag index (PLI) is used to determine if one signal consistently leads or lags another signal, using non-zero iCoh which indicates an interaction between signals that cannot be due to volume conduction. PLI measures the

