extent to which a distribution of phase angle differences is distributed toward the positive or negative side of the imaginary axis on the complex plane. Specifically, we employ unbiased weighted PLI⁶² in which angle differences are weighted according to their distance from the real axis. We emulate the moving window approach used in the spectral analyses described above, allowing evaluation of patterns of changes in these measures over time. Phase slope index is also used as a measure of the consistency of directional flow within a frequency by determining if the slope of the phase lag between two processes is positive or negative over several adjacent frequency bins, suggesting the direction of signal flow. To assess directionality of the changes, we will perform multivariate granger causality analysis⁶⁵ Similar to the power, connectivity analysis will be performed both across the time^{16, 41-43, 50, 66} and the trials⁶⁷ and with frequency and time resolution similar to the spectral analysis.

Graph theory is used to characterize global network architecture and the inter-relatedness of the nodes.⁶⁸ We will employ weighted connectivity measures to construct functional network diagrams and extract metrics using the Brain Connectivity Toolbox.⁶⁹ Given only 5 nodes, we will compare the following measures across conditions: node degree, clustering, pathlengths, and identification of hubs. Dynamic Causal Modeling (DCM), implemented in SPM70, is used to evaluate causal network architecture rather than separately evaluating pairs of nodes. DCM identifies the most likely among a set of competing models that best accounts for observed neural dynamics, allowing modeling of missing nodes which is critical since human studies preclude evaluation of every node.

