Statistical Analysis is done using SPSS. We assess the significance of connectivity measures by shuffling data to create a permutation distribution and calculating Monte-Carlo estimates of the significance probabilities and/or critical values using parametric/nonparametric statistical tests. We will explore the correlation between behavioral and LFP metrics, and clinical scores (total and lateralized UPDRS-III) using a multiple linear regression model. To confirm generalization to new data points, a "leave one-out" procedure will be employed and finally a coefficient of determination (R²) and RMS of errors will be calculated for all generalization data. T-tests will be used to compare between conditions. To investigate interactions, two factor ANOVA will be used. Gaussian "v-test" and Rayleigh tests will be used to compare the preferred phase angle of connectivity with the uniform distribution to infer phase specificity.⁷¹ The Watson-Williams two-sample test (i.e. circular analogue of the two-sample t-test) will be used to assess whether the mean directions of two groups are identical.

Specific Aim 1:

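### Granger direction is planned with no guard against unequal or state-dependent signal-to-noise ratio, and no rule links it to the other directional measures

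*Combined protocol and SAP*

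**What the plan says.** All of this is in the combined protocol and SAP, section 4.a, Data Analysis.

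- **Granger causality.** Under Measures of Network Coupling: "To assess directionality of the changes, we will perform multivariate granger causality analysis".
- **Phase slope index (PSI).** One sentence earlier: "Phase slope index is also used as a measure of the consistency of directional flow within a frequency", with the slope of the phase lag "suggesting the direction of signal flow".
- **Phase lag index (PLI).** "Phase lag index (PLI) is used to determine if one signal consistently leads or lags another signal".
- **Dynamic causal modelling (DCM).** It "is used to evaluate causal network architecture rather than separately evaluating pairs of nodes", and is chosen for "allowing modeling of missing nodes which is critical since human studies preclude evaluation of every node".
- **Preprocessing (LFP Analyses).** "Bipolar re-referencing of adjacent contacts is used in order to emphasize local and minimize global signals". Sections with artifact are excluded.
- **Significance (Statistical Analysis).** "We assess the significance of connectivity measures by shuffling data to create a permutation distribution".

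The documents give no noise level for any sensor, no SNR check or matching across anesthetic states, no version of Granger causality that is robust to noise, and no rule for disagreement between Granger causality, PSI, PLI and DCM.

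**The concern.** Granger causality asks whether the past of one signal improves prediction of another beyond that signal's own past. Suppose two channels carry the same underlying activity with different amounts of added noise. The cleaner channel's past then helps predict the noisier channel more than the reverse, and the analysis reports flow from clean to noisy although neither drives the other.

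Three features of the plan make this relevant:

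- Cortex is recorded from a subdural strip and the pallidum from the DBS lead, so unequal SNR is plausible.
- The Aim 2 and Aim 3b sample sizes rest on alpha/beta power differing between rest and anesthesia. If signal power moves over a fairly fixed noise floor, SNR moves with it.
- The plan accepts that some nodes go unrecorded, so shared unrecorded input is to be expected. Conditioning on the recorded nodes cannot fully remove it.

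Neurophysiology is the primary outcome of Aims 2 and 3b. A reported change in cortex-pallidum direction across propofol states could therefore be a change in SNR, and the plan has no step that would tell the two apart.

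**Working it through.** **No plan figure to reproduce.** The plan attaches no number to directionality. The simulations borrow 16 patients from Aims 2 and 3b. That figure does reproduce: a two-sided one-sample t-test with d = 0.75 and alpha 0.05 needs N = 16 (power 0.801), and 16/(1 − 0.2) = 20 to recruit.

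**Definitions.** For channels x and y, F(x→y) is the usual log ratio of residual variances without and with the past of x. Net direction is D = F(x→y) − F(y→x). D_rev is the same quantity on time-reversed data, and the contrast is T = D − D_rev. D or T is tested by a one-sample t-test across patients.

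**Why T helps.** Autoregressive Granger causality depends only on auto- and cross-covariances. With a zero-lag common source and independent noise, the cross-covariance is the same at lags +τ and −τ. Reversal leaves it unchanged, so D_rev = D in expectation and T = 0. A real lag breaks that symmetry.

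**Assumptions.** SNR values, noise form (white where specified), oscillator frequency and record length are all assumed. Autoregressive order is 12, at 200 Hz in the two-node work.

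**1. Two nodes, 12 Hz, 60 s, 16 patients, 40 trials per setting; share of trials declaring a direction:**

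| Setting (no true net direction) | SNR | Test of D |
|---|---|---|
| Common unrecorded driver | 2 vs 2 | 2.5% |
| Common unrecorded driver | 3 vs 1.5, 4 vs 1 | 100% |
| Symmetric two-way coupling | unequal | 45–60% |

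In the 100% cells the Granger values were 0.13–0.15 one way and 0.05–0.07 the other. T was significant in 2.5–7.5% of trials across the unequal-SNR settings, and in 100% when direction was real.

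**2. Two nodes, 20 Hz, 6000 samples (30 s), 200 runs per cell, noise/signal variance 0.1 to 10; share of single runs with larger F(x→y):**

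- Independent signals: 45–55%, even at 10 vs 0.1. No bias.
- Zero-lag common source, noise 0.1 vs 1: D = 0.2069 − 0.0233 = 0.1836, and the cleaner channel was named driver in 100% of runs. With the noise swapped, D = 0.0232 − 0.2071 = −0.1839, and the direction flipped in 100%. With equal noise the share was 42–49%. At 0.1 vs 1, PSI stayed centred on zero (mean 0.002, SD 0.076) and time-reversed Granger was at chance (52%).
- True one-way coupling x→y: net direction correct in 100% at every noise pair. A spurious reverse term was significant in 100% of runs once driver noise/signal reached 1.
- Lagged copy (40 runs per cell): net direction was mostly wrong only at 5 ms lag with driver noise 3 vs 0.1 (correct in 3–20%; PSI sign correct in 80–100%). At 10–20 ms it was correct in 100%.

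**3. Five nodes, conditional Granger, 16 patients, common unrecorded driver, no interaction.** In one build (60 s, 40 trials per setting) D was falsely declared in 2.5% of trials at equal SNR, 62.5–67.5% at 3 vs 1.5, and 100% at 4 vs 1. A second build gave 100% at both unequal pairs. In the first build, letting SNR change between states produced a false change in direction in 30–87.5% of trials. Inverting the SNR ratio moved mean D from 0.0037 to −0.0043.

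In the first build T gave 0–5% at unequal SNR, 2.5–7.5% for a false change, and 10% (4 of 40) at equal SNR. The Monte Carlo standard error is √(0.05 × 0.95/40) = 0.034, so 10% lies about 1.5 standard errors above 5%. In the second set of runs (two- and five-node) T gave 3–8% and still detected true one-way coupling in 100%.

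**4. Limit of the remedy (set-up 1, 20 trials per setting).** With a zero-lag driver T was significant in 5% of trials. When the unrecorded driver reached the second node 5, 10 or 20 ms later, with no interaction, T was significant in 100% at every SNR pair, including equal SNR. PSI was also significant in 100%, with the same sign.

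**The case against.** A reader might infer that the plan relies on Granger causality alone. It does not: PSI, PLI and DCM are planned, and DCM is the plan's own answer to missing nodes. PSI is also robust in the zero-lag case. But the plan attaches no consequence to a conflict, so a Granger direction can be reported while PSI shows none.

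A reader might also infer that unequal noise creates direction by itself, or that an SNR change under propofol will appear as reversed flow. Neither is supported. Independent signals gave no bias, and true one-way coupling kept its net direction except in the short-lag, very noisy-driver cells. The effect needs shared or coupled activity.

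Bipolar re-referencing deserves credit for reducing shared signal from volume conduction. It does not remove a neural source that feeds both sites. Shuffling tests whether coupling exists, not whether its direction comes from unequal noise.

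It is fair to say that the SNR values are assumed, that Granger causality is one of many coupling measures, and that Aims 2 and 3b are powered on power modulation rather than direction. Conditioning on five nodes also shrinks the effect: net Granger was about 0.004–0.006 in the first five-node build, against about 0.08 with two nodes. The group test still declared it often.

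The strongest objection is that the remedy is incomplete: a lagged unrecorded driver passes both the contrast and PSI agreement. That stands and belongs in the plan.

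**Conclusion.** The concern holds as a conditional one. The plan uses plain multivariate Granger causality for direction, among other directional measures, without a guard against unequal or state-dependent SNR and without a rule joining the measures. Where cortex and pallidum share activity, unequal SNR can produce a false net direction: 100% of two-node trials and 62.5–100% of five-node trials at assumed SNR 3 vs 1.5 or 4 vs 1 with a zero-lag common source. A propofol-related SNR change could then be read as a change in direction.

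The documents do not support the stronger conclusion that the planned directional findings will be wrong or reversed. They give no SNR, and the size of the bias depends on how much activity is shared and at what delays. The analysis should be changed; recruitment and recording need not be.

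**What to change.** Replace the plain Granger test of direction with:

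> Direction, and change in direction across states, is tested as net Granger causality minus net Granger causality of the time-reversed data, per patient and then across patients. A directional claim also requires the same sign on the phase slope index already planned; for a change between states, the change in the phase slope index must have the same sign.

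Add the limit:

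> Neither the contrast nor the phase slope index removes a false direction from an unrecorded driver that reaches the nodes at different delays. Directional claims are conditional on this and are read together with the dynamic causal models.

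The cost is a second run of the same estimation on reversed data and somewhat fewer directional claims. No patients, recordings or operating time are added.

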Aim 1: We estimate our sample size using a Monte Carlo simulation based on predicted differences in propofol sensitivity as defined in prior studies,^{47, 48, 57, 75} which suggest a 20% difference in Ce50 with 20% intersubject variability and an additive measurement error. We performed the Monte Carlo simulation by constructing two population response curves from N patients whose response to propofol was determined by the sigmoidal Emax model while varying only the Ce50 between the populations. The nonlinear fitting was performed for both populations and this process was repeated 1000 times, with the fraction correctly identifying the underlying difference in the model used as our power estimate. N was then incremented until 80% power was obtained, which required approximately 24 patients per arm (total of 48 patients). Similar studies have targeted enrollments of 18-31 subjects per arm.^{47, 48, 76} To account for an estimated 20% dropout rate or protocol error, we plan to recruit a total of 58 subjects. All patients will be recruited from / data collection will occur at UCLA for Specific Aim 1.

Aim 2: Our experiments are purposefully designed to ensure proper power and that experiments can be completed within intraoperative time constraints. Using our prior LFP recordings in PD as well as the published literature^{43, 78, 79}, we conducted a power analysis based on average α/β power modulation between rest and anesthetized state observation (Figure 1). Power analysis indicates a total of 16 patients is required to achieve significant results (one-sample t-test with $d=0.75$, $p=0.8$, $\alpha=0.05$). To account for an estimated 20% dropout rate or protocol error, we plan to recruit at least 20 subjects. Data collection will occur at UTSW and UCLA.

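### The Watson-Williams comparison of preferred phase has no concentration condition, so weak phase preference can be reported as a phase shift

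*Combined protocol and SAP*

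**What the plan says.** Section 4.a, Data Analysis, derives a preferred phase from the phase-amplitude histogram (Measures of Network Coupling). The Statistical Analysis paragraph then plans two steps for it. First, v-tests and Rayleigh tests: "Rayleigh tests will be used to compare the preferred phase angle of connectivity with the uniform distribution to infer phase specificity". Second, a comparison between groups by the Watson-Williams two-sample test, which "will be used to assess whether the mean directions of two groups are identical".

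The paragraph states no minimum concentration, no check that concentrations are similar, and no alternative test. It does not make the Rayleigh result a condition for the second step. A resampling approach, "shuffling data to create a permutation distribution", is planned for connectivity measures. It is not tied to the comparison of mean directions, and parametric tests are allowed beside it.

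The sample-size text for Aims 2 and 3b is based on alpha/beta power, not phase: "Power analysis indicates a total of 16 patients is required to achieve significant results". Each aim then recruits at least 20. Under Study Design (section 3), Aim 2 has a single group of PD patients, and Aim 3b (GPi or GPe stimulation) is compared with Aim 2.

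**The concern.** The F reference distribution of the Watson-Williams test assumes von Mises samples with a common concentration that is not small. A preferred phase can be computed for every patient, even where coupling is absent. If those angles are scattered across patients in one or both conditions, each group's mean direction is largely noise. Two noisy directions will often lie far apart, and the test can read that as a shift.

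Losing a phase preference and moving a preferred phase are different physiological claims. Neurophysiological signals are the primary outcome of Aims 2 and 3b (section 1), so a false statement of the second kind would appear among the main results.

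A separate point concerns design. Contrasts between states in Aim 2 are within patient, and a two-sample test ignores the pairing.

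**Working it through.** **Step 1. The plan's own figure.** Inputs from Sample Size, Aims 2 and 3b: one-sample t-test, d = 0.75, power 0.8, alpha 0.05. With n = 16 the noncentrality is 0.75 × √16 = 3.0, and exact two-sided power is 0.8006. Allowing for 20% dropout, 16 / (1 − 0.20) = 20. Both figures reproduce. They supply the group sizes used below; the documents give no error rate for the phase comparison.

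**Step 2. The statistic.** Let R1, R2 and R be the lengths of the summed unit vectors in group 1, group 2 and both together, and let N = n1 + n2. Then

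F = K (N − 2)(R1 + R2 − R) / (N − R1 − R2), with K = 1 + 3 / (8 κ̂),

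referred to F(1, N − 2). κ̂ comes from the pooled mean resultant length (R1 + R2)/N.

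**Step 3. Why it fails when concentration is low.** With 16 uniform phases the typical resultant is √(16π)/2 = 3.5. Take two such groups whose sample directions happen to differ by 90 degrees:

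- R = 3.5 × √2 = 4.95.
- The pooled length is 7/32 = 0.22, so κ̂ ≈ 0.45 and K ≈ 1.84.
- F ≈ 1.84 × 30 × (7 − 4.95) / (32 − 7) = 4.5, against a critical value F(1, 30) of 4.17.

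Two directions drawn at random differ by more than 90 degrees half the time, so a false-rejection rate near one half is to be expected.

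**Step 4. Simulation.** Assumptions: one phase per patient, von Mises phases, the same mean direction in both groups, nominal 5%, 40,000 replicates per setting (10,000 for 2 vs 0).

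| kappa, group 1 vs group 2 | 16 per group | 20 per group |
|---|---|---|
| 1.5 vs 1.5 | 5% | 5% |
| 2 vs 2 | 5% | 5% |
| 5 vs 2 | 5% | 5% |
| 1 vs 1 | 8% | 8% |
| 5 vs 1 | 9% | 9% |
| 10 vs 1 | 10% | 10% |
| 0.5 vs 0.5 | 22% | 22% |
| 2 vs 0.5 | 19% | 19% |
| 5 vs 0.5 | 22% | 22% |
| 0.25 vs 0.25 | 36% | 39% |
| 10 vs 0.25 | 39% | 40% |
| 0 vs 0 (both uniform) | 44% | 49% |
| 2 vs 0 | 57% | 60% |
| 5 vs 0 | 60% | 63% |

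Kappa 0.5, 1 and 1.5 correspond to mean resultant lengths of about 0.24, 0.45 and 0.60.

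Group sizes also matter. If Aim 3b splits evenly between targets (an assumption), one target against Aim 2 is about 20 vs 10. With the smaller group less concentrated, rejection is then 12% at kappa 10 vs 2 and 19% at 10 vs 1. With the larger group less concentrated (2 vs 10) it is 2%.

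**Step 5. Does the gate work?** The gate requires Rayleigh p < 0.05 and a mean resultant length of at least 0.45 in both groups. The chance of passing the gate and then falsely rejecting, at 16 per group, is 0.1% at 0 vs 0, 0.7% at 0.5 vs 0.5, 3.3% at 1 vs 1, 4.6% at 2 vs 2, 3.2% at 2 vs 0.5 and 5.8% at 5 vs 1. At kappa 2 vs 2, 98% of comparisons pass. Among comparisons that do pass with a true kappa of 0.5 in at least one group, false rejection is still about 19-23%.

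**Step 6. Would permutation be enough?** A permutation p-value for the same statistic gives 4-6% when concentrations are equal, for kappa from 0 to 5. It does not correct unequal concentration: 11-13% at 5 vs 1, 24-26% at 5 vs 0.5 and 62-66% at 5 vs 0.

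**The case against.** The strongest reply is that the plan already looks at uniformity. The v-tests and Rayleigh tests are described immediately before the Watson-Williams test, and a truly uniform group would be non-significant on Rayleigh about 95% of the time. An attentive analyst would see that no preferred phase exists. This has weight, but the plan does not say that the Rayleigh result governs whether directions are compared. Nor does a significant Rayleigh result alone suffice: among runs where both groups pass it, rejection at kappa 0.5 vs 0.5 is still 21-22%.

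The planned permutation approach might also be thought to cover the comparison. The text does not link the two, and Step 6 shows it would repair only the equal-concentration case.

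The following limits stand:

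- The documents give no concentration, so no single error rate can be attached to this trial.
- The figures above about 40% involve a uniform group, for which a common mean direction is undefined. The practical error there is declaring a shift when there is nothing to compare.
- One phase per patient is an assumption. The plan assesses coupling over time and over trials and does not define the unit for the circular tests.
- Preferred phase is one of many coupling measures, and neither aim is sized on it.

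**Conclusion.** The gap is real: the plan names a test that needs at least moderate concentration and sets no condition for using it. Under the assumptions in Step 4, the level is about right from kappa 1.5 upward and drifts to 5-10% when both kappas are at least 1 and group sizes are equal. It rises to about 19-22% when at least one kappa is near 0.5, and further below that.

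A reader might infer more than this in three ways, none of which the documents support:

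- That unequal concentration by itself produces rates of 20-60%. With equal group sizes and both kappas at least 1 it gives no more than about 10%; the high rates need a weakly concentrated group.
- That this trial will have such an error rate. That depends on concentrations the documents do not report.
- That the plan expects phase preference to vanish in some state or under stimulation. Section 1 speaks only of perturbations in how brain signals evolve, and nothing is predicted about preferred phase.

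Severity is minor to moderate. The pairing point for Aim 2 follows from the single-group design; its effect on power was not simulated.

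**What to change.** Add to the Statistical Analysis paragraph of section 4.a:

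1. Mean directions are compared only when the Rayleigh test is significant and the mean resultant length is at least 0.45 in both conditions. Otherwise the report states that there is no preferred phase to compare. This holds the overall false-shift rate at or below about 6% with equal groups of 16 to 20. Because comparisons that pass can still be inflated when true concentration is weak, print both resultant lengths beside every result.
2. For contrasts between states within Aim 2 patients, replace the two-sample test with a circular one-sample test that the mean within-patient phase difference is zero. Keep the two-sample test for independent groups, such as Aim 3b against Aim 2.
3. Report any change in concentration as a separate result, not as a phase shift.
4. State the unit of analysis for the circular tests.

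The change needs a few sentences and no new data. The downside is that some phase comparisons will be reported as not testable. Few are lost when phases are well concentrated (98% pass at kappa 2 in both groups), and more as concentration approaches the threshold.
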